5.3 Treatment Requirements

All eligible patients who consent to this study must have a baseline evaluation (CT or MRI) within 6 weeks of the start of treatment.

Patient must meet all eligibility requirements to be entered onto the protocol.

5.3.1 Duration of Intervention and Evaluation:

Follow-up: A repeat CT scan will be performed after 2 cycles of treatment regimen to evaluate response based on RECIST 1.1 criteria (See Appendix 13.1 for definitions of response) (73). CT scans will be repeated at least every 2 cycles, or 8 weeks, to ensure no progression of disease. Patients will continue on VOR/HCQ or RGF until disease progression, unacceptable toxicity, withdrawal of consent by the patient, or decision of physician for patient's best interest. Crossover to the other arm will be allowed, but OPTIONAL, and will be determined by the treating physician for the patient's best interest. If patient is not given crossover treatment, then the patient will be off study and will be allowed to receive subsequent treatments. Each patient

will be followed for 1 year. We will follow the last patient for 12 months, at which time, the study will be completed for data analysis.

Interim analysis: The O'Brien-Fleming procedure will be used to conduct an interim analyses for efficacy when 50% of the patients complete the study. A statistical basis for stopping the study at the first look will be achieved if the test statistic indicates benefit in the VOR/HCQ Arm and exceeds 2.96259, corresponding to a significance level of 0.003. If the test statistic does not exceed 2.96259 at the first look then the trial will proceed to the final analysis. A treatment effect will be declared significant and beneficial at the final analysis if the test statistic indicates benefit and exceeds 1.96857, corresponding to a significance level of 0.047.

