In refractory mCRC, the role of VEGF inhibition in mCRC patients has not been established (30). Recently, Regorafenib (RGF), an oral multi-kinase inhibitor, including with angiogenic inhibition, was approved for mCRC patients who have failed standard therapies (2). In the CORRECT trial, patients with mCRC were randomized in a 2:1 ratio to receive best supportive care with oral RGF 160 mg or placebo by mouth once daily, for 3 weeks of a 4-week cycle (3). The primary endpoint was overall survival. *Compared to placebo, RGF improved mPFS from 1.7 to 1.9 months ($P<0.000001$) and mOS from 5.0 to 6.4 months ($P=0.005$), regardless of K-RAS status (3).* The most common treatment-related toxicities were fatigue (47% vs 28%, RGF vs placebo), hand-foot syndrome (47% vs 8%), diarrhea (34% vs 8%), anorexia (30% vs 15%), voice changes (29% vs 6%), hypertension (28% vs 6%), oral mucositis (27% vs 4%), rash/desquamation (26% vs 4%), nausea (14% vs 11%), weight loss (14% vs 2%), and fever (10% vs 3%). In this study, 54% patients had grade 3 or more adverse events versus 14% with placebo, with the most common grade 3 fatigue (9% vs 5%) and grade 3 hand-foot syndrome (17% vs <1%). In the third-line setting, even when statistical significance is reached, gains in PFS and OS are modest, i.e., 0.2 months (6 days) improvement in mPFS and the 1.4 months (42 days) benefit in mOS seen with RGF over placebo (3). Given the modest improvements of RGF in survival, VEGF inhibition may not be beneficial to all patients with mCRC refractory to VEGF inhibitors; therefore, more therapies are needed in patients with mCRC progressing despite VEGF inhibition.

2.3 Autophagy as a mechanism for cancer survival:

Autophagy is a conserved protein degradation process that involves the vacuolar sequestration of long-lived cytoplasmic proteins and organelles into a structure called an autophagosome (31).

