5.4.2.2 VOR Dose Modification

Known VOR hematological or non-hematological toxicities will not be attributed to HCQ and will only be attributed to VOR and may result in VOR dose modifications. Toxicities having an attribution to VOR of possible, probable or definite will result in the following VOR dose modifications:

VOR administration will be delayed, reduced or discontinued based on weekly assessment of according to hematological and non-hematological toxicity criteria, as specified below.

If the administration of VOR has to be interrupted, the treatment with HCQ will proceed normally and no catch-up days of VOR. The total number of days of VOR administration and total dose of VOR will be recorded in the CRF.

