5.4.3 Dose Modification for RGF (Table 3)

The starting dose will be RGF 160 mg PO daily, for 3 weeks, of a 4-week cycle, as determined by the phase III study in mCRC patients (3).

Dose can be decreased due to toxicity if deemed by the clinical investigator to be related to RGF. The dose reductions will be 120 mg (level -1), 80 mg (level -2).

Due to known hepatic toxicity, we will monitor liver function tests (ALT, AST and bilirubin) before initiation of RGF and monitor at least every two weeks during the first 2 months of treatment. Thereafter, monitor every cycle or more frequently as clinically indicated. Monitor liver function tests weekly in patients experiencing elevated liver function tests until improvement to less than 3 times the ULN or baseline. Temporarily hold and then reduce or permanently discontinue RGF depending on the severity and persistence of hepatotoxicity as manifested by elevated liver function tests or hepatocellular necrosis. See below for specific recommendations:

Interrupt Regorafenib for the following:

- NCI CTCAE Grade 2 hand-foot skin reaction (HFSR) [palmar-plantar erythrodysesthesia (PPE)] that is recurrent or does not improve within 7 days despite dose reduction; interrupt therapy for a minimum of 7 days for Grade 3 HFSR
- Symptomatic Grade 2 hypertension
- Any NCI CTCAE Grade 3 or 4 adverse reaction

Reduce the dose of Regorafenib to 120 mg:

- For the first occurrence of Grade 2 HFSR of any duration
- After recovery of any Grade 3 or 4 adverse reaction
- For Grade 3 aspartate aminotransferase (AST)/alanine aminotransferase (ALT) elevation; only resume if the potential benefit outweighs the risk of hepatotoxicity

Reduce the dose of Regorafenib to 80 mg:

- For re-occurrence of Grade 2 HFSR at the 120 mg dose
- After recovery of any Grade 3 or 4 adverse reaction at the 120 mg dose (except hepatotoxicity)

Discontinue Regorafenib permanently for the following:

- Failure to tolerate 80 mg dose
- Any occurrence of AST or ALT more than 20 times the upper limit of normal (ULN)
- Any occurrence of AST or ALT more than 3 times ULN with concurrent bilirubin more than 2 times ULN
- Re-occurrence of AST or ALT more than 5 times ULN despite dose reduction to 120 mg

- For any Grade 4 adverse reaction; only resume if the potential benefit outweighs the risks

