For Cycle 1, for patients who are assigned to VOR/HCQ arm, if baseline labs were done <14 days from C1D1, then can omit CBC, CMP, CEA and LDH. Upon randomization, regorafenib prescription will be sent to specialty pharmacy. If the patient receives the medication in <14

days, then the patient can start at home. This start date will be C1D1. If the patient receives ≥ 14 days, then the patient will need a C1D1 clinical visit and labs: CBC, CMP, CEA, LDH.

Repeat EKG after cycle 2 only if clinically relevant

Ω For Cycle 1 Day 15 and Cycle 2 Day 15, we will check CBC and CMP to evaluate for toxicity. Specifically, for RGF, we will monitor ALT, AST and bilirubin. For VOR, we will monitor blood counts. History and physical exam only as needed or if clinically indicated.

± Baseline CT should be Day -36 to Day -1. Every other cycle CT scans can be done +/- 4 days. Off treatment CT scan is done if not done at disease progression or in the last 28 days. (See Appendix 13.1 for definitions of response).

* ONLY required for patients receiving HCQ on study: If the patient is randomized to VOR/HCQ arm, and the patient is 70 year or older or has baseline ophthalmologic pathology (i.e., diabetic retinopathy), then a comprehensive eye exam will be done at baseline. If the

patient continues to receive HCQ on study at 6 months, a repeat comprehensive eye exam will be done at 6 months and then every 6 months while receiving HCQ on study. If the patient has visual disturbances while receiving HCQ, then an ophthalmologic evaluation will be done at that time. If the ophthalmologist recommends discontinuation of HCQ due to eye toxicity, then the patient will be taken off study for toxicity.

Patients receiving RGF are not required to have baseline or follow- up eye exams, unless there is crossover to the VOR/HCQ arm. If patient moves onto VOR/HCQ crossover arm, eye exam is as stated above (patient is 70 year or older or has baseline ophthalmologic).

∞ At baseline, archival tissue from diagnosis, but if not available, we need documentation of mCRC. Pre-cycle 2 tumor biopsy is optional. Follow instructions in **section 5.8.** ¶ Baseline should be done within 14 days of starting Cycle 1. Pre-cycle 2 and Off Treatment blood draws can occur +/- 3 days. Blood samples will be collected in five tubes: Two - 10-ml EDTA tubes for plasma, and Three - 8 mL Vacutainer CPT tubes for PBMCs. Follow instructions in **section 5.8.**

% NCI-CTCAE v4.0 will be used to document adverse events

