6.2 Measurement of Effect

For the purposes of this study, patients should be reevaluated for response every **8 weeks**.

Definitions

Response and progression will be evaluated in this study using the new international criteria proposed by the Response Evaluation Criteria in Solid Tumors (RECIST) Committee. Changes in only the largest diameter (unidimensional measurement) of the tumor lesions are used in the RECIST criteria (73). Note: Lesions are either measurable or non-measurable using the criteria provided below. The term "evaluable" in reference to measurability will not be used because it does not provide additional meaning or accuracy.

See Appendix 13.1 for RECIST criteria

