10.0 Statistical Section

Analytic plan for primary objective:

mPFS-1: Historically, the mPFS for previously treated mCRC patients treated with RGF is 1.9 mos. We predict VOR/HCQ will improve mPFS to 3.8 months. We expect 5% lost to followup. Assuming a 36-month accrual period with 1 year for follow up, 36 subjects per group are necessary to obtain 80% power. With 5% lost to follow-up the sample size required per group is 38 ($=36/0.95$), therefore, the total required sample size is 76 subjects. As a result, the target accrual rate is 3-4 patients/month to achieve a target accrual at 36 months with an additional 12month follow-up.

Treatments will be contrasted with regard to PFS-1 with a proportional hazards model with adjustment for age, sex, race, and the baseline tumor K-RAS status (mutated, wild type); the adjusted hazard ratio, its 95% confidence interval, and the p-value for testing the null hypothesis that the log hazard ratio is zero will be presented. Survival curves will be illustrated with Kaplan-Meier plots. Interactions between treatment and baseline covariates will be explored.

If a patient does not complete Cycle 1 and is off study, then this patient will not be evaluable for efficacy but will be evaluable for toxicity.

Interim analysis: The O'Brien-Fleming procedure will be used to conduct an interim analyses for efficacy when 50% of the patients complete the study. A statistical basis for stopping the study at the first look will be achieved if the test statistic indicates benefit in the VOR/HCQ Arm and exceeds 2.96259, corresponding to a significance level of 0.003. If the test statistic does not exceed 2.96259 at the first look then the trial will proceed to the final analysis. A treatment effect will be declared significant and beneficial at the final analysis if the test statistic indicates benefit and exceeds 1.96857, corresponding to a significance level of 0.047. If a treatment effect is not declared at the interim analysis, a statistical basis for stopping the study for futility will be attained if the conditional power is less than or equal to 20%.

Analytic plan for secondary objectives:

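### CT timing is stated on two clocks, treatment cycles and 8 calendar weeks, with no rule for a delayed cycle; if RGF cycles slip more often, PFS-1 can be biased against VOR/HCQ

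*Combined protocol and SAP*

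**What the plan says.** **Scan timing.** Section 5.3.1, like the synopsis, places the first repeat CT after two cycles and continues: "CT scans will be repeated at least every 2 cycles, or 8 weeks, to ensure no progression of disease". The calendar in Section 6.0 (Table 4) lists tumor evaluation under every other cycle, and its CT footnote adds: "Every other cycle CT scans can be done +/- 4 days". Section 6.2, repeated in Appendix 12.1, does not mention cycles: "patients should be reevaluated for response every" 8 weeks.

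**Holds.** For a VOR interruption, Section 5.4.2.2 says "the treatment with HCQ will proceed normally and no catch-up days of VOR". For RGF, Section 5.4.3 requires interruption for any grade 3 or 4 reaction, and "interrupt therapy for a minimum of 7 days for Grade 3 HFSR". It does not say whether the cycle count or the scan moves. VOR/HCQ treatment can also be held (Sections 5.4.2.1 and 8.0), and Section 5.4.1 allows delay for major events without naming an arm.

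**Endpoint and design.** Under Section 5.7, PFS-1 runs from the start of the first randomized treatment to progression or the off-study date, whichever comes first. Section 10.0 compares the arms with a proportional hazards model and assumes: "Historically, the mPFS for previously treated mCRC patients treated with RGF is 1.9 mos"; "We predict VOR/HCQ will improve mPFS to 3.8 months".

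**The concern.** Progression found on CT takes the date of the CT. If a cycle is delayed by a week, a site using Table 4 can scan at week 9 and comply. A site using Section 6.2 would regard the same scan as outside the +/- 4-day window. Neither is told which is right.

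This matters for the comparison only if delays differ by arm. The text leaves room for that: a VOR-only hold leaves HCQ running with no catch-up days, whereas RGF interruptions are mandatory for defined events and nothing keeps the RGF cycle count going. RGF progression could then be dated later for reasons unrelated to efficacy. The stake is power in a trial of 76 patients designed for 80%.

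**Working it through.** **1. Reproduce the plan's sample size.** Inputs (Section 10.0): medians 1.9 and 3.8 months, 80% power, 36 months accrual plus 12 months follow-up, 5% loss. Two-sided alpha of 0.05 is assumed, because none is stated for the sample size.
- HR = 1.9/3.8 = 0.50 under exponential times.
- Freedman: (1.960 + 0.842)² × ((1 + 0.5)/(1 − 0.5))² = 7.85 × 9 = 70.6, so 71 events.
- Event probability with uniform accrual: 0.999 (RGF) and 0.983 (VOR/HCQ), mean 0.991.
- 71/0.991/2 = 35.8, so 36 per group; 36/0.95 = 37.9, so 38 per group and 76 in total. The plan's figures reproduce. (Schoenfeld gives 66 events, or 34 per group.)

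**2. Where the first scan falls.** 8 weeks = 56/30.44 = 1.84 months. With a median of 1.9 months, the share progressed by then is 1 − 2^(−1.84/1.9) = 0.49. About half of RGF progressions would therefore be dated by that single scan, and a short shift moves them behind the VOR/HCQ events dated at week 8.

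**3. Simulate a slip.** Settings: 36 per arm, exponential times, all progression found by scan, scans every 56 days +/- 4 days, censoring at one year, unadjusted Cox model with Efron ties, critical value 1.96857 (the plan's final boundary), 3,000 runs per row (error about 1 point). One hold pushes the patient's scan series back. The documents give no hold rates, so two adverse-event rates from the phase III RGF trial in Section 2.2.1 serve as proxies: 17% (grade 3 hand-foot syndrome) and 54% ("54% patients had grade 3 or more adverse events versus 14% with placebo").

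| Patients slipping, RGF / VOR/HCQ | Slip | Estimated HR | Power |
|---|---|---|---|
| 0 / 0 | none | 0.50 | 78% |
| 17% / 0 | 7 days | 0.52 | 75% |
| 17% / 0 | 14 days | 0.51 | 74% |
| 54% / 0 | 7 days | 0.56 | 61% |
| 54% / 0 | 14 days | 0.54 | 67% |
| 54% / 27% | 14 days | 0.53 | 71% |
| 54% / 54% | 14 days | 0.50 | 78% |

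Without the +/- 4-day scatter the pattern is the same: 78% with no slip, 73-75% at 17%, 61-65% at 54%.

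A 14-day slip is not worse than a 7-day slip. Either one moves first-scan RGF events behind week 8, but a later first scan also catches some progressions that would otherwise wait for the second scan.

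**4. Vary the assumptions.** Separate runs (800 and 1,000 per setting, 7-day slip, error about 1.5 points) gave:
- no slip: 77-78%;
- 17% of RGF only: 75-76%;
- 54% of RGF only: 64%;
- 54% of RGF and 30% of VOR/HCQ: 72-74%;
- 54% of RGF only, with 30% of events dated off-scan: 69-73%.

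**5. No true difference (both medians 1.9 months; settings of step 3).** The estimated HR is 1.00 with no slip, 1.04-1.05 at 17% and 1.16-1.17 at 54% of RGF only. False findings for VOR/HCQ fall from 3.1% to 1.6-1.7% and 0.2-0.5% respectively.

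**The case against.** The strongest reply is that the plan already contains a calendar interval. Sections 6.2 and 12.1 say 8 weeks, Section 5.3.1 mentions 8 weeks alongside cycles, and a site that follows this produces no bias. That stands as a reason to say the comparison *can* be biased. It does not remove the gap, because Table 4 is also protocol text and supports the other reading.

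Second, delay of the RGF cycle is inferred from silence in Section 5.4.3. RGF is given for three weeks of a four-week cycle, so some holds may overlap the off week without moving the next cycle. VOR/HCQ treatment can also be held or delayed. All of this stands, and it narrows the likely difference between arms; with equal slips the bias disappears.

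Third, the 54% is an adverse-event rate from another trial and not a hold rate, and PFS-1 also ends at off-study dates that no scan determines. Both stand: the 54% rows are an upper scenario, and off-scan dating weakens the effect.

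A reader might go further and infer that the trial could falsely declare VOR/HCQ superior. The direction is the opposite, as step 5 shows. A reader might also infer an inflated type I error from nominally significant results favoring RGF, which rise from 2.6% to 4-11% in the same null simulations. But Section 10.0 declares an effect only when the statistic indicates benefit, and the stated hypothesis is better efficacy of VOR/HCQ, so such a result is not a success under the plan.

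**Conclusion.** The two clocks, and the absence of a rule for when they differ, are in the text. The bias is conditional: it needs sites to follow the cycle clock and RGF cycles to be delayed more often than VOR/HCQ cycles. If both hold, PFS-1 is biased against VOR/HCQ and power is lost.

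From about 78%, power falls to 74-76% (HR 0.51-0.52) if 17% of RGF patients alone slip, and to 61-67% (HR 0.54-0.56) if 54% do, over slips of one to two weeks with +/- 4-day scatter. It is about 72-74% if 30% of VOR/HCQ patients also slip by a week, and unchanged if both arms slip equally. These figures rest on assumed slip shares and lengths, one hold per patient, exponential times and an unadjusted model. The documents do not support a statement that the comparison is biased as it stands, or any single figure for the loss. A clarification is worthwhile because it removes the dependence on these unknowns at little cost.

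**What to change.** State one rule in the synopsis, Section 5.3.1, Table 4 and its CT footnote, Section 6.2 and Appendix 12.1: CT every 8 weeks +/- 4 days, counted on the calendar from C1D1 in both arms, regardless of dose holds or cycle delays. C1D1 matches the current start of PFS-1. Record the reason for every unscheduled scan. A sensitivity analysis of PFS-1 that treats progression as interval-censored, or uses scheduled scan dates, would be a useful addition.

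The cost is protocol wording. Dosing rules are unchanged and the number of scans is essentially the same. The downside is that some scans will not coincide with a cycle visit.

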5.3.2 VOR and HCQ Administration

The starting dose will be VOR 400 mg PO daily and HCQ 600 mg PO daily, as determined by the phase I study in advanced cancer and as given in the expansion cohort of mCRC patients.

Dose can be decreased due to toxicity if deemed by the clinical investigator to be related to VOR. The dose reductions will be 300 mg (level -1), 200 mg (level -2).

Dose can be decreased due to toxicity if deemed by the clinical investigator to be related to HCQ. The dose reductions will be 400 mg (level -1), 200 mg (level -2).

If toxicity is thought to be due to VOR and HCQ, then dose reductions can be done for each drug as above.

Table 2: Dose reductions for VOR plus HCQ in the Phase II study of VOR/HCQ versus RGF in previously treated mCRC patients

If toxicity due to both VOR and HCQ:		
Dose Level	VOR	HCQ
0 (Standard Daily Dose)	400 mg	600 mg
-1	300 mg	400 mg
-2	200 mg	200 mg

If toxicity due to VOR:		
Dose Level	VOR	HCQ
0 (Standard Daily Dose)	400 mg	600 mg
-1	300 mg	600 mg
-2	200 mg	400 mg

If toxicity due to HCQ:		
Dose Level	VOR	HCQ
0 (Standard Daily Dose)	400 mg	600 mg

-1	400 mg	400 mg
-2	300 mg	200 mg

5.3.3 RGF Administration

The starting dose will be RGF 160 mg PO daily, for 3 weeks, of a 4-week cycle, as determined by the phase III study in mCRC patients (3). All patients will be given a handout on how to take Regorafenib (Appendix 12.3).

Dose can be decreased due to toxicity if deemed by the clinical investigator to be related to RGF. The dose reductions will be 120 mg (level -I), 80 mg (level -2).

Table 3: Dose reductions for RGF in the Phase II study of VOR/HCQ versus RGF in previously treated mCRC patients

If toxicity due to RGF:	
Dose Level	RGF
0 (Standard Daily Dose)	160 mg
-1	120 mg
-2	80 mg

5.3.4 Concomitant Medications and Supportive Care Guidelines

Diarrhea Management: Treat diarrhea promptly with appropriate supportive care, including loperamide. Instruct patients to begin taking loperamide at the first signs of: 1) poorly formed or loose stool, 2) occurrence of more bowel movements than usual in one day, or 3) unusually high volume of stool. Loperamide should be taken in the following manner: 4 mg at first onset of diarrhea, then 2 mg after each unformed stool. Daily dose should not exceed 16 mg/day.

Loperamide should not be taken prophylactically. Advise patients to drink plenty of clear fluids to help prevent dehydration caused by diarrhea. Avoid loperamide if there is the presence of blood or mucus in the stool or if diarrhea is accompanied by fever. If grade 3 or 4 diarrhea develops, discontinue further treatment with vorinostat.

Anti-emetic Prophylaxis: During dosing, promethazine (25 mg PO) or metoclopramide (10 mg PO) every 6 hours may be initiated, as needed. For patients who suffer diarrhea, promethazine rather than metoclopramide must be used. For patients who experience nausea and vomiting despite this antiemetic treatment, dexamethasone (4 mg PO) every 12 hours and granisetron (1 mg PO) QD, or equivalent 5HT3 antagonist, may be administered. All patients should have antiemetic medications available once discharged from the clinic. Oral anti-emetic medications should be prescribed and administered as needed, and adjusted during the cycle at the discretion of the treating investigator. The prophylactic use of a 5-HT3-antagonist can be administered before VOR administration if deemed indicated by the investigator. Due to its interaction with P450 enzymes, aprepitant use should be avoided. If needed, then its use must be recorded. Control of nausea and vomiting may require institution of multiple anti-emetic medications including phenothiazines or 5-HT3 antagonists.

Hydration Management: Adequate hydration is important in the event of dysgeusia. Advise patients that popsicles and Gatorade may be useful in this event.

Corticosteroids: If the patient receives steroids an effort will be made to keep the patient on this steroid dose until the next scan is obtained. Corticosteroid dose can be tapered as clinically indicated if the patient appears to be responding to therapy as judged by serial scans.

Anti-convulsants: Because HCQ has known effects on P450 enzymes, patients requiring anticonvulsants may be treated with any of the non-enzyme inducing anti-convulsants, which include: felbamate, valproate acid, gabapentin, lamotrigine, tiagabine, topiramate, zonisamide, or levetiracetam. Patients requiring the use of enzyme-inducing anti-epileptic medication (phenytoin, carbamazepine, phenobarbital, primidone or oxcarbazepine) are not eligible for entry into the study. If these agents are required during the study, patients will discontinue study treatment.

Growth factors: Patients are allowed to continue hematological growth factors such as Aranesp if initiated before the protocol. G-CSF or GM-CSF will not be allowed as prevention in cycle 1, but could be used as needed for treatment of grade 4 or complicated neutropenia on cycle 1 or beyond. If prophylaxis is considered necessary by the clinical investigator beyond cycle 1, this is allowed.

Given the possibility of metabolic interaction through the P450 2D6 enzyme the concomitant administration of HCQ with digoxin, B blockers, cyclosporine and cimetidine should be closely monitored.

